7.5 Analysis of Safety

All analysis of safety will be presented by treatment group for the SAF unless specified otherwise.

The safety data will be summarized relative to the date of the first study drug injection through day 380 from the transplantation day. The safety data that was measured through day 380 will be included. This analysis window will accommodate the protocol visit windows.

7.5.1 Adverse Events

The coding dictionary for this study will be MedDRA. Treatment-emergent adverse event will be defined as an adverse event observed on the day or after the first injection up to 1 year post-transplant. If the adverse event occurs on the day of the first injection of study drug and the investigator marks as “Onset after first dose of study drug” or the onset check box is left blank in eCRF, then the adverse event will be considered treatment emergent. An overview table will include the following for the SAF, mSAF and xSAF :

- Number and percentage of subjects with at least one TEAEs,
- Number and percentage of subjects with drug related TEAEs,
- Number and percentage of subjects with serious TEAEs,
- Number and percentage of subjects with serious drug related TEAEs,
- Number and percentage of subjects with TEAEs leading to death,
- Number and percentage of subjects with drug related TEAEs leading to death,
- Number and percentage of subjects with TEAEs leading to permanent discontinuation of study drug,
- Number and percentage of subjects with related TEAEs leading to permanent discontinuation of study drug, and
- Number of deaths (on or before transplant Day 365 and after Day 365).

The number and percentage of subjects with TEAEs will be summarized for each treatment group. Summaries will be provided for:

- TEAEs by SOC, HLT and PT (for SAF, mSAF and xSAF populations)
- TEAEs by SOC, PT and CTCAE Grade
- TEAEs by severity (mild, moderate and severe)
- TEAEs by relationship to study drug assessed by investigator (Unlikely, possible and probable)
- serious TEAEs assessed by investigator and including Astellas always SAE,
- study drug related (possible and probable) TEAEs assessed by investigator
- study drug related (possible and probable) serious TEAEs by investigator and including Astellas always SAE
- TEAEs leading to permanent discontinuation of study drug,
- study drug related (possible and probable) TEAEs leading to permanent discontinuation of study drug
- TEAEs by PT in descending order of overall will be summarized
- TEAEs, PTs that equal or exceed a threshold of 5.0% in any treatment group, after excluding serious adverse events.

For the same event, a subject reports different severity, the worst severity will be counted.
For the same event, a subject reports different study drug relationship, the highest degree of relationship will be counted.

Adverse Events of Interest

Adverse events of interest are as follows.

- Systemic reactions assessed by the sponsor medical review
- Late onset reactions assessed by the sponsor medical review
- Allergic and demyelinating reactions, to be identified using MedDRA SMQs for demyelination and anaphylactic.
- Local reactogenicity: AEs that are deemed by the Investigator as being associated with a local reactogenicity events. These are identified by a check box in the AE eCRF.
- Acute local vaccine reactions, including injection site Pain, Tenderness, Erythema/Redness, and Induration/Swelling are assessed by the Investigator for 60 minutes after each injection. For each subject, the reported grade on each scale following each injection, and overall the worst grade for each scale reported during the study will be summarized.

7.5.2 Local Reactogenicity Assessed by Subject

Local (non-acute) vaccine reactions, including injection site Pain, Tenderness, Redness, and Swelling or Hardening are assessed by the subject for each of the 7 consecutive days following each injection beginning approximately 24 hours after the dose (day 1-7 post dose). Local reactogenicity assessments will be summarized by treatment. For each subject, the worst reported grade on each scale observed following each injection and overall during the study will be summarized by treatment.

7.5.3 Clinical Laboratory Evaluation

Clinical laboratory data from central will be summarized by treatment group for SAF and mSAF. The baseline value for clinical laboratory evaluations is the last non-missing measurement taken prior to, or on the same day as, the initial injection of study drug.

Quantitative measurements from hematology and biochemistry will be summarized descriptively (n, mean, standard deviation, minimum, maximum and median for each treatment group at each visit). Additionally, a within-subject change will be calculated as the post-baseline measurement minus the baseline measurement and summarized.

Each laboratory result from central laboratory will be classified as low (L), normal (N), or high (H) at each visit according to the laboratory supplied reference ranges. The number and percentage of subjects below and above reference range will be summarized for each treatment group at each visit. Additionally, for medically important parameters, shifts from baseline to post-baseline in either the Low or High direction, and at Final Visit, will be summarized. The post-baseline category will be determined by taking the lowest or highest category for a subject, depending on direction of worsening. The Final Visit will be the last value of a subject within the analysis period.

7.5.3.1 Liver function tests

The liver function test parameters from central laboratory will be assessed by the categories listed below. The number and percentage of subjects who meet the following criteria at post-baseline will be summarized.

- ALT **or** AST > 3xULN, > 5xULN, > 10xULN, >20xULN
- ALT > 3xULN, > 5xULN, > 10xULN, >20xULN
- AST > 3xULN, > 5xULN, > 10xULN, >20xULN
- ALP > 1.5xULN, >3xULN
- Total Bilirubin >2xULN
- (ALT **or** AST > 3xULN) **and** Total Bilirubin > 1.5xULN
- (ALT **or** AST > 3xULN) **and** Total Bilirubin > 2xULN
- (ALT **or** AST > 3xULN) **and** ALP < 2xULN **and** Total Bilirubin > 2xULN

Any subjects who have at least one post-baseline value will be included in this summary. A subject may be counted more than once as the categories are not mutually exclusive (i.e., a subject with a value >10xULN will be counted also in the subsequent categories). The last 3 criteria will be evaluated using the ALT and/or AST assessments that are conducted within 3 days of the Total Bilirubin and ALP assessments, as applicable.

7.5.4 Vital Signs

The baseline value for vital signs is the last measurement taken prior to the initial injection of study drug.

Vital signs [systolic blood pressure (SBP), diastolic blood pressure (DBP), pulse rate, respiratory rate, temperature and weight] will be summarized using mean, standard deviation, minimum, maximum and median by treatment group and visit. Additionally, a within-subject change will be calculated per visit and scheduled time as the post-baseline measurement minus the baseline measurement and summarized by treatment group and visit.

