## **5 TREATMENTS AND EVALUATION**

### **5.1 Dosing and Administration of Study Drugs and Other Medications**

#### **5.1.1 Dose/Dose Regimen and Administration Period**

One (1) mL of 5 mg/mL ASP0113 or placebo will be administered to the subjects at the clinical site when there is no medical contraindication to an IM injection, in the deltoid muscle, alternating sides with each dose if possible. Preparation of study drug will be described in the Pharmacy Manual for the study. The syringes will be masked to maintain the study blind.

The platelet count must be  $\geq 50000/\text{mm}^3$  (spontaneously or after platelet transfusion) performed by the local laboratory within 3 days prior to all study drug injections. Prior to all study drug injections, confirmation must be made that there is no medical contra-indication to an IM injection. Results received in an equivalent local unit of measure must be converted to SI units. If the subject's platelet count does not meet this threshold at the time of the visit, the subject may return for the study drug injection and local reactogenicity assessment at a later time within the allowable window for the visit. If the subject's platelet count does not meet this threshold during the visit window, the dose must be skipped, and the reactogenicity assessment and dose follow-up visit(s) should not be done.

Doses will be given at the following time points:

- Dose 1 at day -14 to -3 pretransplant, within 72 hours prior to the start of chemotherapy and radiation therapy for conditioning.
- Dose 2 at day 14-40 (but not prior to day 14).
  - Dose 2 is to be administered as close to day 14 as possible. If the subject cannot be dosed by day 40 based on these criteria, V5 procedures (except study drug injection and local reactogenicity assessment) is to be completed within 5 days of day 40 (day 40 to 45) and V6 should be skipped.
- Dose 3 at day 60 ( $\pm 5$  days)
- Dose 4 at day 90 ( $\pm 10$  days)
- Dose 5 at day 180 ( $\pm 10$  days)

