### **5.4.1 Vital Signs**

Vital signs (systolic and diastolic blood pressure, pulse rate, respiratory rate, temperature and weight) will be collected at all dosing visits, and at screening (V1), V13 and V14. Height will be collected at screening only.

Vital signs will be collected as follows:

- Vital signs will be collected immediately prior to injection and 60 ( $\pm 10$ ) minutes post injection (except weight) at study visits accompanied by injection.
- Vital signs will be collected once at screening (V1), and at V13 and V14.

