#### **5.4.2.1 Local Reactogenicity Assessments**

Subjects will be evaluated for local reactogenicity and systemic signs for 60 minutes ( $\pm 10$  minutes) after each injection. Subjects will be directly observed for 15 minutes following the injection for any injection-related side effects, then remain in a designated area at the study site for 45 minutes so that side effects can be noted and treated, if necessary.

Local reactogenicity will also be evaluated for each of the 7 consecutive days following each injection. The assessments for each of the 7 consecutive days following an injection will be done by the subject and reported to the site via diary. When reactogenicity is reported as an AE, it must be followed until resolution or medically stable. All local reactions  $\geq$  Grade 3 [Appendix 7] require confirmation by a health care professional.

Grading of reactogenicity will be done using the protocol-specified reactogenicity scale [Appendix 7]. The daily maximum measurement of local reactogenicity signs will be recorded.

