2. Screening procedures may be completed -30 to -5 days prior to the day of transplant. Local laboratory results are to be used for screening purposes. The screening laboratory results may be repeated 1 time throughout the noted period. The subject may be rescreened 1 time if the transplant is delayed and it will be outside the 25 day screening window. If outside the 25 day screening period, all screening procedures must be repeated.
3. Subjects will be assigned a subject number for use throughout the study at the screening visit via the Interactive Response Technology (IRT) system.
4. Screening visit and V2 (first dose of study drug) may occur either separately or on the same day.
5. A complete physical examination (PE) will be conducted at the screening (V1) and at the primary study period completion/day 365 visit (V14). At all other visits where a PE is performed, symptom-directed PEs may be done. A detailed description of the subject’s current disease status and conditioning regimen (including doses) will be recorded at the baseline visit (V2). The evaluations conducted at each visit are to be performed by the Investigator or qualified medical personnel who routinely perform these evaluations in this subject population. Vital signs will be collected immediately prior to injection and 60 (±10) minutes post injection (except weight) at study visits accompanied by injection and once at screening (V1), and at V13 & 14. Vital signs include blood pressure, pulse rate, respiratory rate, temperature and weight. Height will be collected at the screening visit. Performance status will be assessed using the Karnofsky Performance Scale (KPS) at baseline visit (V2).
6. All concomitant medications and therapies administered from 30 days prior to transplant through 30 days post last dose of study drug will be collected on the electronic case report form; Concomitant medications and therapies associated with Grade 3 and higher grade adverse events (AEs) as well as all serious adverse events (SAEs) will be collected from 31 days post last dose of drug through 1 year post-transplant. Over-the-counter medications, and herbal remedies do not need to be captured beginning 30 days after the last dose of study drug.

Footnotes continued on next page

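### At doses 2 to 5 the planned vital-sign tables measure change only from the pre-dose-1 reading, so they cannot show the spread or extremes of the 60-minute post-injection change

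*SAP*

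**What the plan says.** SAP 7.5.4 defines a single reference: "The baseline value for vital signs is the last measurement taken prior to the initial injection of study drug". Blood pressure, pulse, respiratory rate, temperature and weight "will be summarized using mean, standard deviation, minimum, maximum and median by treatment group and visit", and in addition "a within-subject change will be calculated per visit and scheduled time as the post-baseline measurement minus the baseline measurement".

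The readings come in pairs. Protocol 5.4.1 states that "Vital signs will be collected immediately prior to injection" and again at 60 (±10) "minutes post injection (except weight) at study visits accompanied by injection" (the latter wording is from footnote 5 to the SAP's schedule of assessments, which repeats the protocol's footnote).

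The SAP's list of key terms also ties baseline to the first dose. Protocol 7.5 says only that vital signs will be summarised on the safety analysis set. Neither document plans a change from the pre-injection reading of the same visit.

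**The concern.** A reading taken an hour after an injection is there to show what the injection did in that hour. The natural comparator is the reading taken just before it. At dose 1 the plan makes that comparison, because the pre-injection reading is normally the baseline. At the other four injections it compares the 60-minute reading with one taken weeks to months earlier, before conditioning and transplant. That difference mixes the transplant course with any acute effect.

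The wording about scheduled time does not cure this. It separates the pre-injection from the 60-minute reading on the post-baseline side, but the reference stays at the initial injection.

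At stake is a by-arm view of acute changes in blood pressure, pulse, respiratory rate and temperature at doses 2-5 that were not reported as adverse events. Under Protocol 5.5.1 an abnormal reading becomes an adverse event only if it causes signs or symptoms, needs intervention, interrupts dosing or is judged clinically significant. Changes below that bar appear only in the vital-sign tables.

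**Working it through.** The plan states no figure on this point, so there is none to reproduce.

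**1. Age of the reference.** Protocol 5.1.1 places "Dose 1 at day -14 to -3 pretransplant". The later windows are days 14-40, 55-65 (60 ±5), 80-100 (90 ±10) and 170-190 (180 ±10). The shortest gap is the window start plus 3 days; the longest is the window end plus 14.

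| Dose | Shortest gap (days) | Longest gap (days) |
|---|---|---|
| 2 | 14 + 3 = 17 | 40 + 14 = 54 |
| 3 | 55 + 3 = 58 | 65 + 14 = 79 |
| 4 | 80 + 3 = 83 | 100 + 14 = 114 |
| 5 | 170 + 3 = 173 | 190 + 14 = 204 |

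**2. What the planned tables determine.** Let P and Q be the pre-injection and 60-minute changes from the dose-1 baseline. The acute change is Q − P.

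- Mean(Q − P) = mean Q − mean P, provided the tables are split by scheduled time and the same subjects contribute.
- SD(Q − P) = √(SD_P² + SD_Q² − 2·r·SD_P·SD_Q). The correlation r is not tabulated.
- The minimum and maximum depend on the pairing of readings within subjects, which is not tabulated either.

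A check on 250 simulated subjects: keep the planned change-from-baseline summaries fixed (60-minute change: mean −1.57, SD 13.57, range −39 to 45) and re-pair the subjects. The mean acute change stays at −2.0. One pairing gives SD 0 and range −2 to −2; the other gives SD 18.9 and range −49 to 59.

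**3. Size, under assumptions.** The documents give no vital-sign SD, no correlations and no number dosed at doses 2-5. Assumed: systolic pressure SD 15 mmHg at each reading; same-visit correlation ρs = 0.8 (range 0.7-0.9); correlation of each reading with the dose-1 baseline ρb = 0.4 (range 0.2-0.6); 200 dosed per arm.

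- True paired SD = 15·√(2(1 − ρs)) = 9.5 mmHg (6.7 at ρs 0.9, 11.6 at ρs 0.7).
- With every planned SD known, a valid correlation matrix requires only that ρs lie between 2ρb² − 1 and 1. The paired SD is therefore bounded to 0 to 15·√(4(1 − ρb²)). The upper limit is 27.5 mmHg at ρb 0.4, 24.0 at ρb 0.6 and 29.4 at ρb 0.2.

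**4. Visibility of one acute fall.** Simulation: trivariate normal readings (baseline, pre-injection, 60-minute), 20,000 trials per setting, one subject's 60-minute reading lowered by the stated amount. The table gives the share of trials in which that subject is the arm minimum on the paired change, and the share in which the subject is the minimum on at least one planned summary (60-minute value or change from baseline, split by scheduled time).

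| n per arm | Fall (mmHg) | ρs, ρb | Paired | Planned |
|---|---|---|---|---|
| 200 | 40 | 0.8, 0.4 | 91% | 59% |
| 200 | 40 | 0.7, 0.6 | 74% | 72% |
| 200 | 40 | 0.9, 0.2 | >99% | 54% |
| 200 | 30 | 0.8, 0.4 | 65% | 34% |
| 200 | 30 | 0.7, 0.6 | 44% | 45% |
| 200 | 30 | 0.9, 0.2 | 94% | 30% |
| 200 | 50 | 0.8, 0.4 | 99% | 82% |
| 200 | 50 | 0.7, 0.6 | 92% | 91% |
| 200 | 50 | 0.9, 0.2 | >99% | 76% |
| 125 | 40 | 0.8, 0.4 | 93% | 66% |
| 250 | 40 | 0.8, 0.4 | 90% | 57% |

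Even when the subject is the minimum on a planned summary, a low 60-minute value does not by itself show that the fall was acute.

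**The case against.** Change from the pre-treatment baseline is conventional, matches the SAP's own definition and is also used for laboratory data. No objective, endpoint or decision rule calls for a paired change, so SAP 7.5.4 delivers what Protocol 7.5 promises. That is true. The point is an improvement to a descriptive table and does not correct a departure from the protocol.

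The safety purpose is largely met elsewhere. Protocol 5.4.2.1 says "Subjects will be evaluated for local reactogenicity and systemic signs for 60 minutes" after each injection. SAP 7.5.1 adds sponsor review of systemic reactions and a standard anaphylaxis query. Protocol 6.2 directs the monitoring committee's attention to hypersensitivity, and Protocol 3.5 stops dosing for anaphylaxis of grade 3 or higher. This also stands, and it is why the matter is minor. None of these safeguards tabulates vital-sign changes.

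The placebo arm goes through the same transplant course, so comparing 60-minute values between arms remains fair. That is correct, and no bias is claimed. The comparison still lacks the spread and extremes of the acute change.

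The size rests on assumptions. At correlations 0.7 and 0.6 the gain almost vanishes, and with a same-visit correlation of 0.6 and a baseline correlation of 0.4 the paired summary does slightly worse for a 40 mmHg fall (58% against 61%). The upper SD limit of 27.5 mmHg needs a same-visit correlation of 2(0.4²) − 1 = −0.68, which is implausible for readings an hour apart. Both criticisms are fair. The bound shows what the tables fail to determine; it is not a realistic range.

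Finally, the difference can be computed later from individual data. It can, but a table specified before unblinding is better than one requested afterwards.

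**Conclusion.** The concern holds, as a minor one. The texts are clear: one reference before dose 1, paired readings at every injection, and no same-visit change planned. The gaps of 17-54, 58-79, 83-114 and 173-204 days follow from the protocol windows alone. So does the algebra: at doses 2-5 the planned tables can yield at most the mean of the acute change, and not its SD, minimum or maximum.

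The practical size is uncertain. It depends on an assumed SD, assumed correlations, the number dosed and tables split by scheduled time. Across the settings in the main table, the advantage of the paired summary for a 40 mmHg fall runs from 2 percentage points (74% against 72%) to more than 45 (over 99% against 54%). Efficacy, type I error and the capture of clinically evident reactions are unaffected.

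**What to change.** In SAP 7.5.4, add for each of the five injections the 60-minute minus same-visit pre-injection change in systolic and diastolic pressure, pulse, respiratory rate and temperature. Summarise it by dose and treatment group with n, mean, SD, median, minimum and maximum. Weight is excluded because it is not taken at 60 minutes. Keep the change from the dose-1 baseline for long-term trends.

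The cost is one sentence in the SAP and one extra table. Both readings are already collected, so nothing is added for sites or subjects.

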7.5.5 Pregnancies

A detailed listing of all pregnancies will be provided.

7.6 Analysis of PK

Not applicable.

7.7 Analysis of PD

Not applicable.

7.8 Safety Subgroups of Interest

The treatment emergent adverse events will be summarized by the treatment group for the subgroups defined based on the categorized variables listed below:

Grouping variable	Subgroups
Donor/Recipient Relatedness	Related Not Related
Donor CMV Serostatus	Positive Negative
Age group	Age < 65 years Age ≥ 65 years
Sex	Female Male
Race	White Black or African American Asian Other
Geographic Region	North America Europe Asia Australia

7.9 Interim Analysis and Early Discontinuation of the Clinical Study

Futility analyses will be conducted while the study is blinded by an independent data analysis center (DAC). Sponsor personnel will not have access to unblinded interim analysis data during the study unless the futility criterion is met and the sponsor needs to make a decision on discontinuing the trial.

7.9.1 Data Monitoring Committee

A DMC, independent of the Sponsor and Investigators, will be established to review the safety data throughout the study and to assess the futility of the study (See Section [7.9.2](#)). The independent DMC statistician will have access to the randomization schedule. The DMC statistician and a separate independent data analysis center (DAC) will create or coordinate the unblinded deliverables for use by the DMC. The Sponsor will not have access to the unblinded tables and listings created for the DMC.

For details of the DMC refer to the DMC Charter.

7.9.2 Futility Analyses

Futility analyses were conducted according the pre-specified plans described in the DMC Charter. See DMC Charter for additional details.

7.10 Handling of Missing Data, Outliers, Visit Windows, and Other Information

7.10.1 Missing Data

For the primary efficacy endpoint, the various sensitivity analyses will be conducted in order to assess the impact of missing data as described in the sections above.

For the endpoints where the time to event approach is used, a subject without an event will be censored according to the description planned for each endpoint.

For all-cause mortality, subjects with unknown survival status by day 365 will be counted as dead in the crude summary.

The start and stop dates of AEs and concomitant medication will be imputed to determine whether a medication is prior and/or concomitant and to determining whether an AE is/is not treatment emergent. Listings of the AEs and concomitant medications will present the patient reported partial dates; imputed dates will not be shown.

In case of missing partial start and stop dates for concomitant medications, the following rules will be used:

If the start date is missing or partial:

- if the month is missing, use January
- if the day is missing, use the first day of the month under consideration
- if the year is missing, use year of the informed consent date
- if the entire date is missing, use informed consent date

If the stop date is missing or partial:

- if the month is missing, use December
- if the day is missing, use the last day of the month under consideration
- if the year or the entire date is missing, set the stop date to December 31st, 2099

If the imputed start date is after the stop date, then the imputed start date will be 1 day prior to the stop date.

For AEs, a missing or incomplete onset date will be imputed according to the following conventions.

If an onset date is missing or only the year is known, the imputed onset date will be the date of first dose of study drug.

If only the year is known for the AE onset date, the imputed onset date will be the latest of the following non-missing dates:

- Date of first dose of study drug
- January 1 of the year of AE onset date

If only the month and year is known for the onset date, set the surrogate onset date to the first day of that month and then apply the following rules.

- If the month and year of the onset date is prior to the month and year of the first dose of study drug, then the surrogate onset date will be the imputed onset date.
- If the month and year of the onset date is on or after the month and year of the first dose of study drug, then the imputed onset date will be the **latest** of the following non-missing dates:
 - Date of first dose of study drug
 - Surrogate onset date

If the imputed onset date is after the adverse event end date, the imputed onset date will be the same as the adverse event end date.

No imputation of missing data for other variables will be done.

